7.2.2 Exclusion criteria related to the active comparator and/or mandatory background therapies

- E 33. All contraindications to the ezetimibe or warning/precaution of use (when appropriate) as displayed in the respective National Product Labeling
- E 34. All contraindications to the background statins or warning/precaution of use (when appropriate) as displayed in the respective National Product Labeling.

7.2.3 Exclusion criteria related to the current knowledge of alirocumab

- E 35. Known hypersensitivity to monoclonal antibody or any component of the drug products
- E 36. Pregnant or breast-feeding women
- E 37. Women of childbearing potential not protected by highly-effective method(s) of birth control and/or who are unwilling or unable to be tested for pregnancy

NOTE: Women of childbearing potential must have a confirmed negative pregnancy test at screening and randomization visits. They must use an effective contraceptive method throughout the entire duration of the study treatment, and for 10 weeks after the last intake of IMP (injection or capsule, whichever come last), and agree to repeat urine pregnancy test at designated visits. The applied methods of contraception have to meet the criteria for a highly effective method of

birth control according to the ‘Guidance on nonclinical safety studies for the conduct of human clinical trials and marketing authorization for pharmaceuticals’ (45). Postmenopausal women must be amenorrheic for at least 12 months.

8 STUDY TREATMENTS

8.1 INVESTIGATIONAL MEDICINAL PRODUCT(S)

Sterile alirocumab drug product will be supplied at a concentration of 75 mg/mL and/or 150 mg/mL both as 1 mL volume in an auto-injector.

Sterile placebo for alirocumab will be prepared in the same formulation as alirocumab without the addition of protein as 1mL volume in an auto-injector.

Ezetimibe 10 mg tablets over-encapsulated.

Match placebo for over-encapsulated ezetimibe tablets.

NOTE: in order to ensure the continuity of the study treatment without interruption (only in the event the manufacturer faces any performance or supply issues of the auto-injector), contingency alternatives are:

- in case of disruption of the 150 mg auto-injector only, if the use of 75 mg auto-injectors is maintained, patients will need to administer 2 injections as follows:
 - 2 injections of 75 mg as 1 mL each in an auto-injector for patients receiving the 150 mg dose,
 - 1 injection of 75 mg as 1 mL in an auto-injector plus 1 injection of placebo as 1 mL in an auto-injector for patients receiving the 75 mg dose,
 - 2 placebo injections as 1 mL each in an auto-injector for patients receiving placebo.

OR

- in case of disruption of either 75 mg or 150 mg or both auto-injectors, patients will be switched to the use of prefilled syringes of placebo, 75 mg and 150 mg, with one injection of 1 mL for each of these doses.

Should this occur, the alternative IMP will be maintained until the end of the study.

8.1.1 Route and method of administration

A manual for alirocumab IMP administration (injection instruction manual) will be provided to patients containing detailed instructions on use. Also, an administration package containing gauze, alcohol swabs, Band-aids, etc will be provided to the patients.

The alirocumab IMP could be administered by self-injection or by another designated person (such as a spouse, relative, etc). The used auto-injector will be discarded in a sharps container which will be provided to patients. It is recommended that the IMP injections be rotated within an anatomical area (eg, right abdomen then left abdomen). If another concomitant drug is being

injected in the abdomen, then the patient should be advised to use a different part of the abdomen for administration of the IMP.

Patients will be asked to store the alirocumab IMP in a refrigerator (DO NOT FREEZE). Prior to administration, the IMP should be set outside in a safe location at room temperature for about 30 to 40 minutes. Thereafter, the IMP should be administered as soon as possible.

Instructions as outlined above should be provided to the patient (or another designated person [such as spouse, relative, etc] who will administer the injections) at training and as needed during the course of the study. Close supervision and feedback should be given at the training visit, randomization visit, and other visits as needed. Anyone that plans to administer IMP must be trained by the study staff.

8.1.2 Timing of administration

A training injection is planned on Week -1 (V2) with a placebo for alirocumab. A second training injection with placebo for alirocumab may be administered between Week -1 and randomization visit.

During the double-blind treatment period, alirocumab or placebo for alirocumab will be administered SC Q2W, starting at Week 0 continuing up to the last injection (Week 22) 2 weeks before the end of the DBTP. If the injection is scheduled to take place on the same date as the site visit, then the IMP should be administered after the blood sampling has been completed.

Further training with the scheduled double-blind alirocumab IMP can be done between W 0 and W 4 and at additional scheduled or unscheduled visits, as per investigator's judgment.

Double-blind IMP will start as soon as possible after the call for randomization using the treatment kit number provided by the IVRS/IWRS. The first injection after randomization will be done at the site by the patient or another designated person (such as spouse, relative, etc) under direct site staff supervision. Patients will be monitored at the investigational site for at least 30 minutes after this first double-blind injection.

Alirocumab IMP injection should be administered Q2W SC at approximately the same time of the day; however it is acceptable to have a window period of ± 3 days. The time of the day is based on patient's preference.

If by mistake or due to other circumstances an injection is delayed by more than 7 days or completely missed, then the patient should return to the original schedule of study treatment administration without administering delayed injections. On the other hand, if the delay is less than or equal to 7 days from the missed date, then the patient should administer the delayed injection and then resume the original schedule of study treatment administration.

Ezetimibe 10 mg or placebo for ezetimibe capsules will be taken orally once daily at approximately the same time of the day, with or without food. Preferably, on the injection days the IMP capsule will be administered roughly at the time of injection (either before or shortly after). The capsules must be taken until the day before the end-of-treatment visit (early or not), and not stopped at the time of the last injection.

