10.2 DEFINITION OF SOURCE DATA

Evaluations that are reported in the e-CRF must be supported by appropriately signed identified source documentation related but not limited to the following:

- Agreement, date, and signature of informed consent mentioning the study identification.
- Patient identification, last participation in a clinical trial, medical history, associated diseases, and data related to the studied pathology.
- Contraception methods for women of childbearing potential.
- Previous and concomitant medication (including the LMT).
- Study identification.
- Treatment number, dates of administration.
- Dates of visits and assessments including the examination report.
- Vital signs, height, body weight.
- Faxed central lab reports (dated and signed by the Principal Investigator or Subinvestigator).
- IVRS/IWRS confirmation fax (screening, screen failure, training kit allocation, randomization, treatment reallocation, discontinuation, end of DBTP, end of study, unblinding if applicable).
- ECG records signed and dated.
- AEs and follow-up:
 - In case of SAE, the site should file in the source document at least copies of the hospitalization reports and any relevant examination reports documenting the follow-up of the SAE.
- Date of premature study discontinuation (if any) and reason.

Source documentation may be found in the following:

- Patient's identity.
- Medical history.
- Hospital records.
- Nursing notes.
- Physician's notes.

10.3 HANDLING OF PATIENT TEMPORARY OR PERMANENT TREATMENT DISCONTINUATION AND OF PATIENT STUDY DISCONTINUATION

The IMP should be continued whenever possible. In case the IMP is stopped, it should be determined if the stop can be made temporarily; permanent IMP discontinuation should be a last resort. Any IMP discontinuation should be fully documented in the e-CRF and source notes. In any case, the patient should remain in the study as long as possible.

Pregnancy will lead to definitive treatment discontinuation in all cases.

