10.3.1 Temporary treatment discontinuation with investigational medicinal product(s)

Temporary treatment discontinuation (also referred to as treatment interruption) may be considered by the Investigator because of suspected AEs. Reinitiating of treatment with the IMP will be done under close and appropriate clinical and/or laboratory monitoring once the Investigator will have considered according to his/her best medical judgment that the responsibility of the IMP in the occurrence of the concerned event was unlikely and if the selection criteria for the study are still met (refer to [Section 7.1](#) and [Section 7.2](#)).

All treatment interruption duration should be recorded by the Investigator in the appropriate e-CRF screens when considered as confirmed.

Treatment interruption is defined as one or more scheduled injections or one or more capsules that are not administered to the patient as decided by the Investigator.

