10.3.2 Permanent treatment discontinuation with investigational medicinal product(s)

Permanent treatment discontinuation (also referred to as treatment discontinuation) is any treatment discontinuation associated with the definitive decision from the Investigator or the patient not to re-expose the patient to the IMP at any time.

Patient withdrawal from the study treatment or study should be avoided as much as possible.

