10.3.3 List of criteria for permanent treatment discontinuation

The patients may withdraw from treatment if they decide to do so, at any time and irrespective of the reason, or this may be the Investigator's decision. All efforts should be made to document the reasons for treatment discontinuation and this should be documented in the e-CRF.

Patients should discontinue the IMP for the following reasons:

- Pregnancy, intention for pregnancy, or no longer with effective contraceptive method of birth control (females only).
- Acute injection reaction of clinical concern.
- Serious adverse event (or non-serious but severe in intensity) of hypersensitivity reaction considered related to IMP.
- At patient request "i.e., withdrawal of the consent for treatment"
- If, in the investigator's opinion, continuation with the administration of the IMP would be detrimental to the patient's well-being.
- Intercurrent condition that requires discontinuation of the IMP (eg, laboratory abnormalities, please refer to decision tree [Appendix D](#)).
- At the specific request of the Sponsor.
- Any code breaking requested by the Investigator.
- Patient receives double-blind treatment prior to randomization

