10.4.5 Guidelines for reporting adverse events of special interest

10.4.5.1 Reporting of adverse events of special interest (AESI) with immediate notification

For these AEs, the Sponsor will be informed immediately (ie, within 24 hours), as per SAEs notification described in [Section 10.4.4](#), even if not fulfilling a seriousness criterion, using the corresponding screens in the e-CRF.

- ALT ≥ 3 ULN (if baseline ALT <ULN) Or ALT ≥ 2 times the baseline value (if baseline ALT \geq ULN) (Please refer to related flowchart in [Appendix D](#)).
- Allergic events
 - General allergic drug reactions and/or local injection site reactions deemed to be allergic (or have an allergic component) that require consultation with another physician for further evaluation of hypersensitivity/allergy, as per the investigator's medical judgment or as per [Section 10.6.2](#), should be reported as an AESI with immediate notification. These reactions require completion of the specific e-CRF screen (see [Section 10.6.2](#))
 - General allergic events, and all injection site reactions require completion of the specific e-CRF screen (see [Section 10.6.2](#)), regardless of requirements for immediate reporting.
- Hemolytic anemia (See [Section 10.4.6.1](#) and [Appendix E](#))
 - If there is a decrease in Hb and reflexive testing as per [Appendix E](#) suggesting hemolysis, then report this as an AESI with immediate notification. Special e-CRF screen will need to be completed.
- Pregnancy
 - Pregnancy occurring in a female patient enrolled in the clinical trial will be recorded as a pre-specified AE with immediate notification and IMP should be discontinued in all cases. It will be qualified as an SAE only if it fulfills the SAE criteria. The follow-up of the pregnancy will be mandatory until the outcome has been determined.
 - Pregnancy occurring in a female partner of a male patient enrolled in the clinical trial, if permitted by the female partner and by local regulatory policies, pregnancy will be recorded as a pre-specified AE with immediate notification. The pregnancy will be qualified as an SAE only if it fulfills the SAE criteria and should be followed-up until the outcome has been determined.
- Symptomatic Overdose with IMP
 - Alirocumab or placebo for alirocumab:

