10.6.2 Allergic adverse events

See [Section 10.4.5.1](#) and [Section 10.4.5.2](#).

Specific e-CRF screens are to be filled in to assess allergic reactions or allergic-like reactions that may occur during the clinical studies conducted with alirocumab.

Sometimes transient injection site reactions, irritant in nature, may occur, requiring no intervention and being of uncertain significance. These reactions would not be considered to be allergic reactions.

AEs that may constitute an allergic reaction (eg, generalized itch, nasal itch, swelling at injection site, flushing, hives, swelling at lips, eyes, face, tongue, hands, feet, lump in throat, difficulty to swallow, hoarseness, change in pitch of voice, incapacity to speak, wheezing, chest tightness, stridor) should be considered to be reported on the General Allergic Reaction and/or Local Injection Site Reaction Complementary Form.

AEs that are obviously not of allergic origin (eg, local injection site reactions) should only be recorded on the Local Injection Site Reaction Complementary Form. However, injection site reactions which progress/expand/worsen/etc should be evaluated as recommended in [Section 10.6.2.1](#) and General Allergic Reaction Complementary form should be completed.

The IMP should be immediately interrupted (temporarily discontinued) if there is a suspicion of an allergic event related to IMP. See [Section 10.3.1](#) for further information on treatment interruption and [Section 10.3.3](#) for criteria for permanent treatment discontinuation.

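### Protocol 8.1.2 keeps capsules going until an early end-of-treatment visit with no exception for mandated permanent stops, and where capsules do stop at once the 5-day visit target outlasts the 3-day on-treatment limit

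*Protocol*

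**What the plan says.** **Dosing rule.** Protocol 8.1.2 states that capsules "must be taken until the day before the end-of-treatment visit (early or not), and not stopped at the time of the last injection". It gives no exception and does not refer to the stopping rules.

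**Stopping rules.** Protocol 10.3.2 defines permanent discontinuation as a "definitive decision from the Investigator or the patient not to re-expose the patient to the IMP at any time". Three triggers matter here:
- Pregnancy. Section 10.3: "Pregnancy will lead to definitive treatment discontinuation in all cases". Section 10.4.5.1: "IMP should be discontinued in all cases".
- "Acute injection reaction of clinical concern" (10.3.3).
- "Serious adverse event (or non-serious but severe in intensity) of hypersensitivity reaction considered related to IMP" (10.3.3).

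Suspected allergy comes first under 10.6.2: "The IMP should be immediately interrupted (temporarily discontinued) if there is a suspicion of an allergic event related to IMP". That step is temporary.

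**Capsules are IMP.** Protocol 8.1 lists ezetimibe and its placebo among the investigational products. Section 10.3.1 defines an interruption as "one or more scheduled injections or one or more capsules that are not administered to the patient as decided by the Investigator".

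**Early visit.** After a permanent stop, Protocol 10.3.4 keeps the patient in the visit schedule but without study treatment. It asks for an unscheduled visit with the end-of-treatment assessments as soon as can be arranged, with a soft target of 5 days from treatment discontinuation.

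**On-treatment limit.** In Protocol 11.3.1.2 and SAP 2.3.1.2 the efficacy treatment period closes at the earlier of 21 days after the last injection and 3 days after the last capsule.

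**The concern.** The 8.1.2 sentence mainly warns patients not to drop the daily capsule when the two-weekly injections finish. But it also covers an early end-of-treatment visit, and SAP 2.5.3 uses that term for the visit of patients who stop IMP prematurely. A site that looks up capsule dosing in 8.1.2 and finds the word must is told to continue a drug that section 10.3 says has to end. The stops concerned are those where this is least acceptable: pregnancy and serious drug reactions.

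The second issue is one of data. The early visit may be the last LDL-C taken on treatment. If capsules stop at once, a visit that is on time under 10.3.4 can still be too late for the on-treatment definition. The value then leaves the on-treatment estimands, which include the first key secondary endpoint (Protocol 9.1.2.1). For a patient who stops before the Week 4 sample, it could be the only value that would qualify the patient for the mITT population.

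**Working it through.** The plan gives no figure on this point to reproduce. The check is a day count.

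**Inputs.**
- D = day of the decision to stop permanently; the visit is on D+v, with v = 0 to 5 (Protocol 10.3.4).
- If 8.1.2 is followed, last capsule = D+(v−1).
- End of efficacy treatment period = min(last injection + 21, last capsule + 3) (Protocol 11.3.1.2, SAP 2.3.1.2).

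**Which limit decides?** With two-weekly dosing, take the last injection as 0 to 13 days before D. The injection limit then falls between D+8 (−13 + 21) and D+21. The capsule limit is D+3 at the latest when capsules stop at the decision, so it decides.

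**Day count.** Gap = days from last capsule to sample; a gap of 3 or less is on-treatment.

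| Visit | 8.1.2 followed: last capsule | Capsule days after D | Stop at once, last capsule on D: gap | Stop at once, last capsule on D−1: gap |
|---|---|---|---|---|
| D+0 | D−1 | 0 | 0, on | 1, on |
| D+1 | D | 0 | 1, on | 2, on |
| D+2 | D+1 | 1 | 2, on | 3, on |
| D+3 | D+2 | 2 | 3, on | 4, off |
| D+4 | D+3 | 3 | 4, off | 5, off |
| D+5 | D+4 | 4 | 5, off | 6, off |

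**Conflict.** With a visit on D there is none. With a visit on D+1 there is none if that day's capsule was taken before the decision. From D+2 to D+5, obeying 8.1.2 means 1 to 4 days of capsules after a stop that 10.3.2 says admits no re-exposure.

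**Timing.** If 8.1.2 is followed, the sample is always 1 day after the last capsule and there is no gap problem. If capsules stop on D, visits on D+4 and D+5 meet the 10.3.4 target and are off-treatment. If the last capsule was on D−1, D+3 is off-treatment as well. So the two problems do not arise in the same patient: one comes from following 8.1.2, the other from stopping at once.

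**When is a value actually lost?** Three conditions must hold together:
1. The sample is more than 3 days after the last capsule.
2. It falls inside an analysis window in SAP Table 2. No window covers days 127 to 154, for example.
3. It would have been the selected value, that is, the one nearest the target day.

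The documents give neither an early-stop rate nor a distribution of the delay to the early visit, so the number of patients cannot be computed.

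**The case against.** **The rules can be reconciled.** Section 10.3.4 wants the early visit at the time of discontinuation. If it happens that day, everything is satisfied. A pregnancy found by the urine test at a scheduled site visit could be such a case. This stands: the clash needs a mandated stop and a delayed visit. A reader might infer that 8.1.2 and 10.3 can never both be followed; the day count does not support that.

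**The safety sections already settle it.** Section 10.3.4 removes study treatment administration after a permanent stop, 10.3.1 lets the investigator withhold capsules, and 10.3.2 is unambiguous. Sites would probably follow these. A reader might infer that the protocol lacks stopping rules or intends dosing to continue in pregnancy; it does neither. What remains is that 8.1.2 says must, 10.3.3 says should, and 8.1.2 contains nothing to send the site to section 10.3.

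**8.1.2 is itself the alignment.** Where it is followed, the sample lies well inside the 3-day limit. This also stands. A reader might infer that the 5-day target endangers every early stop; it matters only where capsules stop more than 3 days before the sample.

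**Exclusion is the definition working as written.** The 3-day limit is the sponsor's choice, and the visit serves mostly safety assessments, so its target need not match an efficacy cut-off. That is a fair reason to leave the estimand alone. It is no reason to set a lipid target that lets an avoidable loss occur, although the target is soft and permits the gap rather than causing it.

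**Conclusion.** The point holds and is minor. The wording of 8.1.2 is wrong for one situation: a mandated permanent stop followed by an early visit on a later day. A 10.6.2 allergy interruption joins that situation only once it becomes permanent. Voluntary or non-urgent stops can satisfy every rule.

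The timing mismatch is real where capsules stop at once: 2 of the 5 days after the decision (D+4 and D+5) fall outside the on-treatment limit when the last capsule is on D, and 3 (D+3 to D+5) when it was on D−1. This rests on injections being on schedule, so that the capsule limit is the one that applies.

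The consequence is confined to the on-treatment estimands and to the few values that meet all three conditions above. Its size cannot be quantified, and no direction of bias can be shown. A reader might try to turn the analysis windows into a share of samples lost. The windows show only when an early sample could be selected, whatever the capsule gap, so they do not measure the loss.

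A reader might also infer a threat to the primary result. There is none: the primary ITT estimand uses every LDL-C value regardless of adherence (Protocol 9.1.1).

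**What to change.** 1. In Protocol 8.1.2, add to the capsule sentence: *except when IMP is stopped for safety or pregnancy (10.3.1, 10.3.3, 10.4.5.1, 10.6.2), in which case capsules stop at once.*
2. In Protocol 10.3.4, ask for the early-visit lipid sample, if possible, within 3 days of the last capsule. Keep the 5-day target for the other assessments and leave the definition of the efficacy treatment period unchanged.

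The cost is one clause in each section. The first has no practical downside. The second is a slightly tighter soft target for one fasting sample. Since Protocol section 10 has non-fasting patients rebooked, some sites may bring the whole visit forward or see the patient twice. Endpoints, estimands and sample size do not change.
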